examine cognitive function under a variable duration of LFS. We hypothesize that there will be a trend towards improvement in task performance under the LFS setting, measured through reaction time and error rates, and that this improvement will be stable or enhanced with sustained LFS. We hope to utilize these results to inform the design of a larger phase 2 efficacy study. Our specific aims are as follows:

- 1) To monitor the safety of LFS in the STN of patients with PD by examining the psychological, cognitive, and motor consequences of LFS
- 2) To determine the feasibility of utilizing low frequency DBS to improve cognition in patients with PD by examining if there is a trend toward improved executive function with LFS over high frequency stimulation (HFS) and no stimulation settings.
- 3) To further examine feasibility by determining if the differential effects of LFS versus HFS of the STN are long lasting in a small patient group.

At present, DBS stimulators are set at varying stimulation frequencies based on the acute effects of DBS on motor performance, with limited understanding of cognitive consequences. Understanding the effects of different stimulation frequencies on non- motor tasks will help elucidate the mechanism behind cognitive impairment in PD. If our hypotheses are correct it could lead to the development of new treatment plans that involve alternating between low and high frequency stimulator settings to optimize both motor and cognitive domains. Ultimately, focused treatment for cognition may slow the progression from mild cognitive impairment to dementia, improving real world functioning and quality of life.

5) Background

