Treatment for cognitive impairment remains limited. Only rivastigmine has received approval from the FDA for PDD but is only modestly effective (Emre et al 2004). The conventional Dopa Replacement Therapy (DRT) improves motor symptoms but shows mixed effects on cognitive symptoms, improving some, and worsening others, largely due to nonspecific increases in dopamine (Poletti & Bonuccelli 2013). Deep Brain Stimulation (DBS) allows for targeted treatment to specific areas of the BGn. Currently, high frequency stimulation (HFS) is performed in the STN or globus pallidus interna (GPi) and has proved very effective in reducing motor symptoms when DRT has lost efficacy (Volkman 2004), but like its oral counterpart, does not show substantial improvements in cognitive functioning (Halpern et al 2009). Some studies even show worsening function in verbal fluency and some executive function domains (Heo et al 2008). Unlike oral therapy, our understanding of how DBS works to improve BGn functioning remains in its infancy. There are great potentials for adjusting contact locations, stimulation frequency, and other stimulator settings in increasingly complex ways to optimize both motor and non-motor symptoms of PD. For example, the dorsal STN is thought to be more motor related and some propose that spread of current to non-motor regions of the STN may be responsible for cognitive impairments associated with STN DBS. In fact, controlling spread by computational modeling techniques to minimize ventral stimulation prevented some of the cognitive deficits observed with STN stimulation (Frankemolle et al 2010).

Clinical trials using DBS to improve cognition are underway with exciting preliminary reports. HFS of part of the hypothalamus improved cognition in 6 patients with mild Alzheimer's disease, increased activity in downstream circuitry involved in memory, and slowed cognitive decline (Laxton et al 2013, Laxton et al 2010).

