a) Neuropsychiatric tests. We will perform the BDI and NPI at baseline, at the first experimental session, once by telephone call after 24 hours of LFS, and a fourth time at the final experimental session. The score of the BDI will be compared across sessions and a score that rises above 20 will be considered positive for the development of moderate depression. The NPI assesses frequency, change in severity, and caregiver distress over 12 neuropsychiatric domains and we will look for caregiver reports of significant change across these domains.

b) Motor tests. The Unified Parkinson's Disease Rating Scale (UPDRS) will be performed prior to patient's surgery as part of the patient's routine care. We will repeat the scale at the final experimental session to assess changes in motor symptoms after sustained LFS.

c) Changes in cognitive function will also be assessed as described below.

2. Feasibility. Improvement in cognitive function will be measured by three cognitive tests: the Stroop test, the N-Back test, and the verbal fluency test. We will measure reaction time and error rates and look for significant changes across stimulator frequencies. The results from 20 patients will help us determine if a large-scale study of effectiveness is warranted and feasible.

Describe any primary or secondary safety endpoints.

See above.

PROTOCOL TITLE: Safety and feasibility of using low frequency deep brain stimulation of the subthalamic nucleus to improve cognitive performance in patients with Parkinson's disease

12) Procedures Involved

a) Describe and explain the study design.

The study design is a safety and feasibility study. We aim to identify 20 PD patients who will receive bilateral STN DBS as part of their standard care. We plan to measure the safety of LFS in the STN as measured through psychological, cognitive, and motor scales, and compare cognitive performance with low and high frequency STN DBS. We propose that LFS in the theta range will not negatively affect psychiatric symptoms or alter motor symptoms, and will improve performance on tests of executive functioning.

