to rely on connections between the basal ganglia and the prefrontal cortex (Dadgar et al 2013, Jaywant et al 2014). Furthermore, DBS has been shown in some studies to impair phonemic verbal fluency, which may or may not recover over time (Ehlen et al 2014, Wojtecki et al 2006, Wu et al 2014). These specific letters were chosen based on the frequency of English language words that begin with the letters (Borkowski et al 1967.)

Total testing time will be approximately 30 minutes per stimulation condition with 20 minutes between conditions, resulting in a total time of approximately 30 minutes for the baseline cognitive testing, 2 hours for the first experimental session and 30 minutes for the second experimental session. Additional time will be needed for setup and explanation of the task directions. Finally, 20 minutes of psychological screening will be performed at the baseline session, over the phone between experimental sessions 1 and 2, and following cognitive testing during experimental session 2.

Baseline Testing: 30 min cognitive testing, 20 minute psychological screening (Total Time: approximately 50 min)

Experimental Session 1: 20 minutes psychological screening, 2 hours cognitive testing (Total Time: approximately 2h 20 min)

Phone call between experimental session 1 and 2: 20 minutes psychological screening

Experimental Session 2: 30 min cognitive testing, 20 minute psychological screening, 20 min motor screening (Total Time: approximately 70 minutes)

b) Humanitarian Use Device (HUD)

NA

13) Data and Specimen Banking

No data or specimens will be retained longer than required by law or hospital policy.

14) Data Management and Confidentiality

The target sample size is 22 subjects. The study design is a safety and feasibility phase 1 study. While results may show a trend towards efficacy, we will not be able to power the study toward efficacy.

Safety Data Analysis:

To examine possible effects on motor symptoms, we will screen for changes in the motor section of the UPDRS score after sustained LFS. After each patient is tested, we will calculate individual changes in UPDRS scoring. After the entire patient population is tested, we will use T-tests to determine if there is a significant change in the overall rating scale.

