We will also examine changes in psychological symptoms. For each individual patient, we will measure the BDI and NPI at baseline, at the first experimental session, by phone call after 24 h LFS, and at the final experimental session. For the BDI, we will consider any score greater or equal to 20 as evidence of moderate depression and will terminate the study for any individual that shows evidence of depression. At the group level, we will calculate

PROTOCOL TITLE: Safety and feasibility of using low frequency deep brain stimulation of the subthalamic nucleus to improve cognitive performance in patients with Parkinson's disease

the percentage of people that develop depression. For the NPI, we will calculate the total score. At the individual level we will look for the development of new symptoms in the 12 subsections. At the group level we will perform an ANOVA to look for significant changes across the 3 time points.

Cognitive Data Analysis:

The cognitive data analysis will examine the effect of theta frequency stimulation on cognitive task performance. Analyses for the Stroop task will include the examination of response time and error rates across stimulator settings. Two (trial type: congruent vs incongruent) by three (Setting: low, high, no stimulation) ANOVAs will be performed for both reaction time and accuracy. Post conflict and post error reaction time adjustments will also be examined across stimulator settings. For the N-back test, ANOVAs will also be performed to assess the effects of complexity (1,2-back) and stimulation frequency (none, high, low) on error rates. For the verbal fluency test, the average number of words generated across stimulation conditions and the change in word number on low and high frequency stimulation settings will be compared. Analyses will be performed using MATLAB and STATA.

Describe any procedures that will be used for quality control of collected data.

a.) Study-Wide:

NA

b.) Local

Describe the local procedures for maintenance of confidentiality.

This research is partly funded by a donation from the Chevo Foundation. The Chevo Foundation will not have access to any of the study documents including the data.

Data files to be stored include group assignment, background information, any head scans if performed, and results from neurocognitive and motor tests.

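### Aim 2 needs low-frequency stimulation to beat both high-frequency and no stimulation, but no planned test is a directional contrast of low-frequency with no stimulation

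*Combined protocol and SAP*

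**What the plan says.** Section 4 (Objectives), aim 2, asks whether "there is a trend toward improved executive function with LFS over high frequency stimulation (HFS) and no stimulation settings". That is a directional claim against two comparators.

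Section 14, Cognitive Data Analysis, gives the tests:

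- Stroop: "Two (trial type: congruent vs incongruent) by three (Setting: low, high, no stimulation) ANOVAs will be performed for both reaction time and accuracy".
- N-back: "ANOVAs will also be performed to assess the effects of complexity (1,2-back) and stimulation frequency (none, high, low) on error rates".
- Verbal fluency: one sentence with two parts. The first compares average word counts over the conditions. In the second, "the change in word number on low and high frequency stimulation settings will be compared".

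No pairwise or directional contrast is named for any setting. Section 11 (Study Endpoints, Feasibility) is equally non-directional: the investigators will "look for significant changes across stimulator frequencies". It adds that the 20-patient results will help decide whether a large effectiveness study is worthwhile. No rule for that decision is given, and section 7 states that the study is not powered for efficacy.

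On what HFS may do, section 5 (Background), discussing HFS, reports that "Some studies even show worsening function in verbal fluency and some executive function domains". Section 12 says that "DBS has been shown in some studies to impair phonemic verbal fluency".

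On test order, section 12 and Figure 2 put the no-stimulation test first in experimental session 1. Only the order of HFS and LFS is randomised.

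**The concern.** A three-level Setting test asks whether any setting differs from any other, in either direction. Aim 2 asks whether one particular setting is better than each of the other two. The answers diverge in a pattern that the protocol's own background makes plausible: HFS worsens performance and LFS leaves it where it was without stimulation. The Setting test can then be significant although LFS has no effect.

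The second part of the fluency comparison has the same limit. It sets LFS against HFS and does not say whether LFS improves on no stimulation.

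At stake is the wording of the main cognitive finding. A result produced by harm from HFS could be summarised as a cognitive benefit of LFS and carried into the planning of a phase 2 efficacy study.

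**Working it through.** **Plan's own figure.** There is no power calculation to reproduce. The documents give no significance level, SD or effect size for the cognitive outcomes. The only arithmetic is the sample size: 20 analysed + 2 usability subjects = 22, which agrees.

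**Inputs.** From the documents: n = 20, three settings within patient. Assumed: two-sided 0.05; SD of every paired difference = 1, with equal correlations, so the error variance is 1²/2 = 0.5; LFS mean equal to the no-stimulation mean; HFS worse by d = 0.3, 0.5 or 0.7; at first, no practice or fatigue effect.

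**Setting test.** The means (none, LFS, HFS) are (0, 0, −d), with sum of squares about their average 2d²/3. The noncentrality is λ = n × (2d²/3) / 0.5 = 20 × (4d²/3) = 26.67d², on 2 and 38 df, with critical F = 3.245.

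**LFS versus HFS.** Paired t with 19 df, noncentrality d√20, critical value 2.093.

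| Assumed HFS harm d | λ | Setting test significant | d√20 | LFS significantly better than HFS | LFS significantly better than both (simulated) |
|---|---|---|---|---|---|
| 0.3 | 2.40 | 24.6% | 1.34 | 24.6% | 1.7% |
| 0.5 | 6.67 | 59.6% | 2.24 | 56.4% | 2.3% |
| 0.7 | 13.07 | 88.5% | 3.13 | 84.4% | 2.5% |

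The last column uses 100,000 simulated trials per row. LFS is significantly better than no stimulation in 2.5% of trials in every row, as it should be for an inert setting.

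**Fluency.** If both changes are taken from the same reference score R, then (LFS − R) − (HFS − R) = LFS − HFS. The reference cancels, so this part of the comparison carries no information on LFS against no stimulation.

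**How the two-contrast rule must be worded.** With inert LFS and the same HFS harms, requiring only that both point estimates favour LFS is met in about 49% to 50% of trials. The intervals must exclude zero. Applied to four outcomes (Stroop reaction time, Stroop accuracy, N-back errors, fluency; independence assumed), a 2.4% chance each gives 1 − (1 − 0.024)⁴ = 9.3% that at least one passes.

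**Fixed first position of no stimulation.** Keep LFS inert and d = 0.5, and add an assumed practice gain of the same size to both later conditions. Both contrasts are then significant in about 20% of trials for a gain of 0.3 SD and about 40% for 0.5 SD.

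**Price of requiring both.** If LFS truly beats both comparators by 0.5 SD, one contrast is significant in about 56% of trials and both in about 40%. At 0.7 SD the figures are 84% and 75%.

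**The case against.** The strongest reply is that a reader could infer two things that the documents do not support.

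First, that harm from HFS cannot be told apart from benefit of LFS. It can: no stimulation is tested in session 1 and is a level of the Stroop and N-back ANOVAs, and the first part of the fluency sentence compares averages across conditions. The three means would show the pattern to anyone who looked.

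Second, that a significant Setting effect triggers phase 2. No section says so. The results are to help with that decision, the hypothesis in section 4 is worded as improvement under LFS, and power for efficacy is disclaimed. Both points stand. What remains is that nothing commits the investigators to the comparison that aim 2 names.

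An advantage over HFS is also not an empty result. Section 12 plans to compare low with high frequency, aim 3 concerns their differential effects, and section 4 envisages alternating between settings. That stands too: such a finding may merit study, provided that it is not called improvement.

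Part of the support for harm from HFS is weak. Section 12 ties Stroop worsening to DBS placement, which all session 1 conditions share, and its fluency statement does not separate placement from stimulation. The section 5 statement on HFS is the firmer basis, but it gives no effect size.

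**Conclusion.** The concern holds as a mismatch between test and aim, and should be fixed. Aim 2 is directional against two comparators; the named tests are omnibus or, in the second part of the fluency comparison, low against high. With inert LFS and HFS harm of 0.3 to 0.7 SD, the Setting test is significant in about 25% to 88% of trials, against about 2% when LFS must significantly beat both. Those percentages rest on the assumed effect sizes, the common SD and the absence of practice effects. That an omnibus test can be significant without any LFS benefit does not depend on them.

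It is not a fatal flaw: the data needed are already collected, the study is exploratory, and no binding decision hangs on the F test. Naming the missing contrast is necessary but not sufficient, because the fixed first position of no stimulation confounds that contrast with practice or fatigue.

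**What to change.** In section 14, Cognitive Data Analysis:

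1. For each cognitive outcome, including fluency, prespecify two within-patient contrasts, LFS minus no stimulation and LFS minus HFS, each with a 95% interval. The ANOVAs may stay as description.
2. Describe LFS as improving cognition on an outcome only if both intervals exclude zero in favour of LFS. If only LFS minus HFS does, report less impairment than under HFS, which may still merit study.
3. State that the absence of an alpha adjustment is justified only for requiring both contrasts within one outcome. Report every outcome rather than the best one.
4. Either include no stimulation in the randomised order or state that LFS minus no stimulation is confounded with practice or fatigue.

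Cost: items 1 to 3 change wording only and need no extra patients or visits. The price is the lower chance of a positive reading shown above (about 56% to 40% at a true advantage of 0.5 SD). Randomising no stimulation under item 4 changes the session 1 order, and a no-stimulation test that follows a stimulation condition may carry over some of its effect. Stating the limitation costs nothing but leaves the confounding in place.

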Figure 2: Stimulation schedule. The first experimental session (E1) will include 30 minutes of baseline cognitive testing. Stimulation will then be turned on (Stim) for 5 minutes prior to cognitive testing under the first frequency condition (either HFS or LFS depending on randomization) (Cog C1). Stimulation will then be turned off and the patient will have a 15 minute rest period. Stimulation at the second testing frequency condition will then be turned on for 5 minutes and the cognitive testing will be repeated (Cog C2). At the completion of this session, LFS will be turned on for 48 hours. When the patient returns to clinic for the second experimental session (E2) they will repeat cognitive testing after sustained LFS (Cog S-Stim). The stimulation will be turned off and the patients will return home to continue standard care. Shaded boxes represent periods of stimulation.

PROTOCOL TITLE: Safety and feasibility of using low frequency deep brain stimulation of the subthalamic nucleus to improve cognitive performance in patients with Parkinson's disease

[figure not shown]

Figure 3: Safety Measures. Motor, psychological and cognitive tests present for each patient contact are indicated. *This motor test performed by neurologist as part of routine care and occurs at a clinic visit prior to the patient’s anticipated surgery.

We will also identify and enroll two subjects that have PD in order to test the ease of use of the computerized cognitive test, prior to the enrollment of additional subjects. These subjects will perform the computerized cognitive test once and will not participate in any other study procedures. We will use this information to decide on optimal parameters within the computerized cognitive test such as stimulus presentation time and response time allowed.

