Cognitive testing will include three cognitive tests. The first is the single-trial computerized version of the Stroop color-naming task. This task is an executive function task that measures attention and inhibition (MacLeod 1991). Performance on this task has been shown to be impaired in patients with PD. Patients make more errors, have a slower response times, and show increased Stroop interference relative to controls (Brown & Marsden 1988). Furthermore, performance may worsen following STN DBS placement, with further increases in error rates (Jahanshahi et al 2000, Witt et al 2004). Stimuli consist of three color words printed in one of the three colors such that there are congruent trials where the written color word and ink color match, and incongruent trials where the written color word and ink color do not match. Participants are instructed to ignore the written word, and perform one of three key presses corresponding to the color of the written word. They will first be trained to accuracy on the key presses using 100% congruent trials. Patients will be instructed to be both fast and accurate.

The second cognitive test is a computerized version of the N-back test, which has been shown to target working memory. Performance on this task has also been shown to be impaired in patients with PD (Beato et al 2008). Patients will perform 2 blocks of trials corresponding to 1-back, and 2-back. In this task, patients will be asked to make a key press when they see a matching spatial configuration one or two stimuli before the current stimuli.

The final test is the FAS phonemic fluency test. Patients will be asked to verbally name as many words as they can that start with the letters F, A, or S within a 1 minute time period. Patients will perform the verbal fluency test with each of the three letters once in random order after Stroop and N-back computer tasks have been completed. People with PD have been shown to have difficulty specifically with phonemic verbal fluency, which is thought

PROTOCOL TITLE: Safety and feasibility of using low frequency deep brain stimulation of the subthalamic nucleus to improve cognitive performance in patients with Parkinson's disease

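### The N-back asks for a press only on matches but is analysed by undefined error rates, so a change in readiness to press under stimulation can be read as a change in working memory

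*Combined protocol and SAP*

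**What the plan says.** Section 12 (Procedures Involved) introduces a "computerized version of the N-back test, which has been shown to target working memory". It has a 1-back and a 2-back block, in which "patients will be asked to make a key press when they see a matching spatial configuration one or two stimuli before the current stimuli". No response is described for non-matches. The share of match trials and the number of trials per block are not stated. Two pilot subjects are to inform "optimal parameters within the computerized cognitive test such as stimulus presentation time and response time allowed".

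Section 14 (Cognitive Data Analysis) specifies one N-back analysis: ANOVAs "to assess the effects of complexity (1,2-back) and stimulation frequency (none, high, low) on error rates". An N-back error is not defined, misses and false alarms are not separated, and no sensitivity or criterion measure is named. The Stroop analysis in the same paragraph does carry a trial-type factor: "Two (trial type: congruent vs incongruent) by three (Setting: low, high, no stimulation) ANOVAs will be performed for both reaction time and accuracy".

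Section 11 (Study Endpoints) says of the three cognitive tests together: "We will measure reaction time and error rates and look for significant changes across stimulator frequencies". On their use it says: "The results from 20 patients will help us determine if a large-scale study of effectiveness is warranted and feasible". Section 15 also counts cognitive test performance among the safety data.

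**The concern.** In a task where the patient presses only on a match, there are two ways to be wrong: failing to press on a match (a miss) and pressing on a non-match (a false alarm). A patient who becomes more cautious makes more misses and fewer false alarms. A patient who becomes more impulsive does the reverse. Neither change says anything about memory, yet the pooled error rate moves unless the two changes happen to cancel. When matches are the minority, false alarms carry more weight in the pooled rate, so from an unbiased start, pressing less can look like better memory.

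This matters because the settings being compared may themselves alter readiness to press. If they do, a contrast of low frequency stimulation with high frequency or no stimulation can be significant, or can be masked, for reasons unrelated to working memory. The result feeds both the decision on a larger study and the review of cognitive safety.

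**Working it through.** **Inputs.** From the documents: press on matches only; 20 patients; two complexity levels; three settings; outcome error rates. Not in the documents, and therefore assumed: match share t, trial count, sensitivity d', criterion c (positive means less ready to press) and all variances. The plan gives no N-back error rate, effect size or power, so there is no figure of its own to reproduce.

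**Formula.** Under the equal-variance signal-detection model:

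- hit rate H = Φ(d'/2 − c)
- false-alarm rate F = Φ(−d'/2 − c)
- pooled error E = t(1 − H) + (1 − t)F

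**Fixed memory, moving criterion (d' = 1.5, t = 0.3).**

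- c = −0.5: H = Φ(1.25) = 0.8944, F = Φ(−0.25) = 0.4013; E = 0.3 × 0.1056 + 0.7 × 0.4013 = 31.3%
- c = 0: H = 0.7734, F = 0.2266; E = 22.7%
- c = +0.5: H = 0.5987, F = 0.1056; E = 0.3 × 0.4013 + 0.7 × 0.1056 = 19.4%

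An extreme case: at d' = 1.0 an unbiased patient has E = Φ(−0.5) = 30.9%. A patient who never presses has H = F = 0, so E = t = 30.0%, which is slightly better.

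**Dependence on match share (d' = 2.0 throughout).** Pooled error:

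| Match share | c = −0.25 | c = 0 | c = 0.25 | c = 0.5 |
|---|---|---|---|---|
| 20% | 20.2% | 15.9% | 13.0% | 11.5% |
| 30% | 19.0% | 15.9% | 14.2% | 13.9% |
| 50% | 16.6% | 15.9% | 16.6% | 18.8% |

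At c = 0, E = Φ(−d'/2), so an error rate can be converted to the d' of an unbiased patient. Moving from c = 0 to 0.5 looks like a rise in d' from 2.0 to 2.40 with 20% matches, and like a fall to 1.77 with 50% matches. Memory is the same in both. With 50% matches, a shift from 0.25 to −0.25 leaves error at 16.6%.

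**Simulation at d' = 2.0.** 20 patients, 60 trials per setting, between-patient SD 0.5 (d') and 0.3 (c), within-patient SD 0.1 for both, paired t-test of two settings at two-sided 0.05, 4000 runs, no true memory change. Percentage significant, pooled error / d' (log-linear correction):

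| Criterion shift | 20% matches | 30% matches | 50% matches |
|---|---|---|---|
| none (0.25 in both) | 5.1 / 5.4 | 4.9 / 5.0 | 5.0 / 4.8 |
| 0 to 0.5 | 77.7 / 4.9 | 24.6 / 4.9 | 27.5 / 5.8 |
| 0.25 to −0.25 | 97.0 / 6.4 | 75.0 / 4.7 | 5.4 / 4.7 |
| 0.5 to −0.25 | 99.7 / 6.7 | 78.3 / 6.2 | 15.2 / 5.0 |

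Misses alone or false alarms alone do not solve the problem: each was significant in 91-100% of the pure-shift scenarios.

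**Smaller shift, different starting points.** With d' = 1.5 and 30% matches, a shift of −0.3 / +0.3 makes pooled error significant in 57% / 29% of trials from c = 0, but in only 13% / 5% from c = 0.5. The reason is that error is lowest at c = ln[(1 − t)/t]/d' = ln(0.7/0.3)/1.5 ≈ 0.56, and the curve is flat there. Across d' 1.5 to 3, 20-50% matches and c from 0 to 0.5, the range for a 0.3 shift is about 5% to 84%.

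**Limit of d'.** At d' = 3, c = 0.5 and 30% matches, a pure shift of +0.3 makes corrected d' significant in 12% of trials, and +0.5 in 35%.

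**The case against.** The strongest reply has five parts.

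- **Pooling is not stated.** The plan says error rates, in the plural and undefined. This stands as a limit: pooling is the natural reading of a two-factor model without a match factor, but it is an inference.
- **Error rate is not the only measure named.** A reader might infer that it is the sole N-back outcome. Sections 11 and 15 also name reaction time across the cognitive tests, so that is too absolute. What is true is that section 14 specifies no N-back analysis other than error rates. Stroop, given under the same settings, could also reveal a change in impulsivity, but it would not correct the N-back score.
- **A shift in readiness to press is plausible, not documented.** A reader might take the plan to have established it, because the title of one cited reference reports poorer response inhibition under STN stimulation. The body cites that reference only for Stroop errors after DBS placement. Nothing says that the N-back criterion moves, or moves differently at the two frequencies.
- **The size rests on assumptions.** This stands. The high false-positive rates need particular match shares and starting points. The simulation also assumes a common mean shift in all patients and tests one paired contrast, not the planned ANOVA.
- **The stakes are modest.** This is one of three tests in a study which says "we will not be able to power the study toward efficacy", and no decision rule hangs on it. That lowers the priority, but lack of power does not excuse a measure that can respond to the wrong thing.

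**Conclusion.** The concern holds in a limited form. As specified, the N-back score cannot separate memory from readiness to press, and the plan fixes neither the error definition nor the match share that would show whether this matters. A response-bias shift can therefore be read as a working-memory effect of low frequency stimulation, in either direction. The chance of a spurious finding under a 0.3 SD shift runs from nominal (about 5%) to about 84% over the assumed range, so no single figure should be quoted as the expected error.

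The documents do not support saying that the N-back result will be false, that stimulation is known to shift the criterion, or that d' is immune to bias. The conclusion rests on reading error rates as pooled misses and false alarms, and on the equal-variance signal-detection model. The change is worth making because it is a better use of data the task already generates, but it is not a fatal flaw.

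**What to change.** In section 14, name d' as the N-back outcome in the complexity-by-setting analysis. Compute it per patient, level and setting from hits and false alarms, with a stated correction for rates of 0% and 100% (for example log-linear). Report hit rate, false-alarm rate and criterion by setting beside it. Pooled error may stay as a descriptive figure, with an error defined. Fix the match share and trial count per block when the task parameters are settled with the two pilot subjects, before the main patients are tested.

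The cost is a change of wording and the storage of trial-level key presses; no patients or visits are added. The downside is that d' is noisier with few matches and is still somewhat bias-sensitive near ceiling, as an easy 1-back may be. It should therefore be interpreted together with the hit and false-alarm rates.
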